13.5 Record Retention

An investigator or sponsor shall maintain the records required by 21 CFR Part 812.140 during the investigation and for a period of 2 years after the latter of the following two dates: The date on which the investigation is terminated or completed, or the date that the records are no

longer required for purposes of supporting a premarket approval application or a notice of completion of a product development protocol. The Investigator must maintain confidential all study documentation, and take measures to prevent accidental or premature destruction of these documents. All essential documents from the Investigator will be kept in the Investigator binder. All sponsor essential documents will be kept in the study master file. The investigator and sponsor shall also maintain a record of their location of the respective essential documents. If the Investigator's personal situation is such that archiving can no longer be ensured by him/her, the Investigator shall inform the Sponsor and the relevant records shall be transferred to a mutually agreed upon designee.

13.6 Performance Monitoring

Monitors will periodically check questionnaire data to ensure all fields are entered as far as possible and inquire as to whether any usability issues are being encountered as the study progresses.

14 MONITORING, AUDITING, AND INSPECTING

14.1 Study Monitoring Plan

The Investigator agrees to provide reliable and accurate data, and all information requested by the study protocol (with the help of any questionnaire, other appropriate instruments) in an attributable, legible, contemptuous, original, accurate, and complete form according to the instructions provided and to ensure direct access to source documents to Sponsor representatives. Any changes to the sourced data shall be traceable and not obscure the original entry.

The Sponsor of this Study is responsible to Health Authorities for taking all reasonable steps to ensure the proper conduct of this study protocol with regards to ethics, protocol compliance, integrity and validity of the data recorded on the CRF and questionnaires. Thus, the main duty of the Monitoring Team is to help the Investigator and the Sponsor maintain a high level of ethical, scientific, technical and regulatory quality in all aspects of the study.

At regular intervals during the study, the site will be contacted, through monitoring visits, letters or telephone calls, by a representative of the Monitoring Team to review study progress, Investigator and subject compliance with study protocol requirements, and any emergent problems. During these monitoring visits, the following, but not exhaustive list of points will be scrutinized with the Investigator: subject informed consent, subject recruitment and follow-up, Adverse Event documentation and reporting, outcome events documentation and reporting, Investigational Product allocation, Investigational Product accountability, and quality of data.

14.2 Auditing and Inspecting

For the purpose of ensuring compliance with the study protocol, Good Clinical Practice and regulatory requirements, the Investigator should permit inspection by applicable regulatory body authorities. This investigation will not include audits conducted by the Sponsor.

The Investigator agrees to allow the inspectors to have direct access to his/her study records for review, being understood that this personnel is bound by professional secrecy, and as such will not disclose any personal identity or personal medical information.

The Investigator will make every effort to help with the performance of the inspections, giving access to all necessary facilities, data, and documents.

As soon as the Investigator is notified of a future inspection by the authorities, he will inform the Sponsor and authorize the Sponsor to participate in this inspection.

The confidentiality of the data verified and the protection of the subjects should be respected during these inspections.

Any result and information arising from the inspections by the regulatory authorities will be immediately communicated by the Investigator to the Sponsor. The Investigator shall take appropriate measures required by the Sponsor to take corrective actions for all problems found during the inspections.

15 DEVIATIONS

All departures from the approved protocol shall be documented by the Investigator. All deviations will be recorded on the subject CRF, and a deviation report will be sent to Laborie and the ethics board, as required. Timelines for notification will be subject to ethics board standard operating procedures. Deviations will be reviewed and signed off by the sponsor. If deviations are observed/reported that significantly affect or have the potential to significantly affect human subject protection or reliability of the trial results, then LABORIE will conduct a root cause analysis and implement appropriate corrective and preventative actions.

16 AMENDMENTS

If there are any changes to the protocol during the application of the study or during the length of the clinical study in progress, the IRB will be notified for review. During an ongoing study if an amendment is made to the protocol the amended protocol will be sent to the applicable institution within the timelines required. The Investigator should not implement any deviation from, or changes to the clinical protocol without agreement by the sponsor and prior review and documented approval/favourable opinion from the IRB of an amendment, except when necessary to eliminate an immediate hazard(s) to a clinical study subject. In some instances, an amendment may require a change to the Informed Consent Form. The investigator must

receive an IRB approval/favourable opinion concerning the revised Informed Consent Form prior to implementation of the change.

17 STUDY ADMINISTRATION

17.1 Funding Source and Conflicts of Interest

Laborie will be the sponsor and the financial details are covered in the Investigator Agreement.

17.2 Subject Stipends or Payments

Subjects will be offered a \$40 USD stipend for their participation in the study to offset the cost of parking and/or meals required during their clinic visit.

The Sponsor has covered this study by means of an insurance covering bodily injury or property damage arising out of the clinical trial. The certificate of insurance evidencing the coverage, insurance company, policy number and the sum insured are provided in the Study's File.

17.3 Committees

A Data Monitor Committee will not be utilized in this study based on the evaluation of the level of potential risks.

17.4 Study Timetable

PROPOSED STUDY TIMELINE	TOTAL DURATION (WEEKS)	ACTUAL DATES
PROPOSED START DATE (Planning)	8	JULY 10, 2017
PROPOSED SITE TRAINING & INITIATION PHASE	1	NOVEMBER 20, 2017
PROPOSED RECRUITMENT (1 st subject in to last subject out)	12 - 14	NOVEMBER 27, 2017
PROPOSED DATABASE LOCKOUT	4	MARCH 16, 2018
PROPOSED STUDY REPORT COMPLETION	4	MARCH 30, 2018
TOTAL (WEEKS / MONTHS)	34 / 8 ^{1/2}	
ESTIMATED COMPLETION (QUARTER)	Q2 FY2018	APRIL 2018

18 ETHICS AND REGULATORY APPROVAL

This study will not begin until the appropriate approvals from the IRB have been obtained. Any additional requirements imposed by the IRB will be followed. This study will be conducted in

compliance with all international laws and regulations, and national laws and regulations of the countries in which the usability study is performed, as well as any applicable guidelines.

19 PUBLICATION POLICY

The results of the study may be submitted for publication, whether peer-reviewed or marketing materials. Publication rights and details are covered in the Investigator Agreement, there may be other authors involved in the creation of the publication.

20 REFERENCED DOCUMENTS

20.1 Informed Consent Documents

- TDOC5Fr-PEDS-01-AF1 – Pediatric Assent Form [REDACTED]
- TDOC5Fr-PEDS-01-ICF1 – Informed Consent Form [REDACTED]
- TDOC5Fr-PEDS-01-AF3 - Pediatric Assent Form [REDACTED]
- TDOC5Fr-PEDS-01-ICF3 - Informed Consent Form [REDACTED]
- TDOC5Fr-PEDS-01-AF2 - Pediatric Assent Form [REDACTED]
- TDOC5Fr-PEDS-01-ICF2 - Informed Consent Form [REDACTED]
- TDOC5Fr-PEDS-01-HA - HIPAA Authorization [REDACTED]
- TDOC5Fr-PEDS-01-HA - HIPAA Authorization [REDACTED]

20.2 Investigator's Brochure

- TDOC5Fr-PEDS-01-IB T-DOC 5 French Investigator's Brochure

20.3 Case Report Forms:

- TDOC5Fr-PEDS-01-CRF1 - Case Report Form 1
- TDOC5Fr-PEDS-01-CRF2 - Case Report Form 2
- TDOC5Fr-PEDS-01-CRF3 - Case Report Form 3
- TDOC5Fr-PEDS-01-CRF4 - Case Report Form 4

T-DOC® 5 French Clinical Study

STUDY NUMBER:

TDOC5Fr-PEDS-01

STUDY NAME:

T-DOC® 5 Fr Pediatric Clinical Investigation:

A Pivotal Study to Assess the Performance, Safety and Usability of a New 5 French Air-Charged Catheter for Performing Urodynamic Studies on Pediatric Subjects

NCT NUMBER:

NCT03429270

DOCUMENT:

STATISTICAL ANALYSIS PLAN

DOCUMENT VERSION & DATE:

Version 1.0

July 9, 2018

CLINICAL STUDY STATISTICAL ANALYSIS PLAN

DEVICE:

T-DOC® 5 French Air-Charged Vesical and Abdominal Urodynamic Catheters

STUDY NUMBER:

TDOC5Fr-PEDS-01

STUDY NAME:

T-DOC® 5 Fr Pediatric Clinical Investigation:

A Pivotal Study to Assess the Performance, Safety and Usability of a New 5 French Air-Charged Catheter for Performing Urodynamic Studies on Pediatric Subjects

Version 1.0

July 9, 2018

SIGN-OFF

Statistician	Print Name		Date	18 July 2018
	Signature			

This document has been reviewed by LABORIE (Refer to Entropy PRC# 022385).

Contents

Introduction	3
Study Objectives and Endpoints	4
Analysis revisions from the protocol	5
Primary Endpoint	5
Secondary Endpoint	6
Exploratory Analysis	6

Introduction

The purpose of this statistical analysis plan (SAP) is to provide clarification about the statistical considerations and methods to be implemented for the analysis of data from the TDOC5Fr clinical study. This statistical analysis plan is based on protocol version 2.02 (TDOC5Fr-PEDS-01-PR-V2.02). The protocol clearly describes the study endpoints, but the hypothesis testing procedures and criteria for study success requires additional details. The SAP is written by an independent statistician [REDACTED] with no access to or knowledge of accumulating trial data. Any revisions to the SAP will be made prior to database lock and reasons for such revisions will be described in the final clinical study report.

Study Objectives and Endpoints

The following are the objectives and endpoints of the TDOC5Fr-PEDS-01 clinical study:

OBJECTIVES	ENDPOINTS
Primary	
To confirm the T-DOC® 5Fr vesical and abdominal catheters as a safe and effective means of measuring urodynamic pressure in pediatric subjects 12 years of age and younger.	The primary endpoint will be measured by recording the clinician safety and effectiveness rating for each patient on their CRF. The clinician will indicate whether the T-DOC® 5 Fr vesical and abdominal catheters are safe and effective for measuring urodynamics pressure in patients who enrolled and completed the urodynamic procedure.
Secondary	
To evaluate the usability of the device by collecting clinical user feedback and evaluating the following subjective measures using defined ordinal scales: ease of use, ease of insertion, presence of artefacts, stability of the tracing, perceived time savings, ease of voiding around catheter, presence of use errors and overall satisfaction.	The usability performance endpoint will be captured in a questionnaire format. The trained clinical users will rate the T-DOC® 5 Fr performance on a scale of 1-5 on the study outcome questionnaire.
Exploratory	
To explore whether the newly designed, smaller sized T-DOC® 5 Fr catheters causes undue discomfort based on subjective subject feedback regarding the discomfort and pain level, for those able to communicate such feedback.	This exploratory endpoint will be measured by collecting patient feedback (within the abilities of the child) regarding the level of discomfort and pain experienced during their Urodynamic test using the Wong-Baker visual analogue scale. Patients capable of providing feedback on a Visual Analogue Scale, will grade their discomfort/pain at 5 or lower, on the Wong-Baker scale from 0 ("No Hurt") to 10 ("Hurts worst").
To explore the effect of several factors (e.g., age, gender, weight, height) on optimal insertion depth of the T-DOC® 5 Fr catheters.	Subjects' age, gender, weight, and height will be recorded on TDOC5Fr-PEDS-01-CRF1. These data will be analysed to determine a subject stratification approach to be used in examining further hypotheses for later research regarding optimal insertion depth.

Analysis revisions from the protocol

All subjects enrolled and completed the urodynamic procedure will be considered in the final analysis. Enrolled subjects who do not undergo the urodynamic procedure or begin the urodynamic procedure but do not complete it (for any reason determined by the investigator to be unrelated to the T-DOC® 5 Fr catheters) will not be included in the final analysis and can be replaced.

Primary Endpoint

In the statistical analysis plan, the null hypotheses for the safety and effectiveness endpoints are designed to rule out success rates $\leq 75\%$. The hypotheses as stated in the protocol are based on obtaining a point estimate of $\geq 95\%$ rather than bounding the lowest rate that would be consistent with the observed data.

The allowable Type I error (α) for each hypothesis will be 5% (1-sided), and the Type II error is calculated to be 10% (90% power).

Safety and effectiveness will be evaluated separately via the following sets of hypotheses:

Primary Hypothesis for Safety

- H_0 : Clinicians rate T-DOC® 5 Fr vesical and abdominal catheter as safe for measuring urodynamic pressure in $\leq 75\%$ of enrolled pediatric subjects who complete the urodynamic procedure
- H_A : Clinicians rate T-DOC® 5 Fr vesical and abdominal catheter as safe for measuring urodynamic pressure in $> 75\%$ of enrolled pediatric subjects who complete the urodynamic procedure

Primary Hypothesis for Effectiveness

- H_0 : Clinicians rate T-DOC® 5 Fr vesical and abdominal catheter as effective for measuring urodynamic pressure in $\leq 75\%$ of enrolled pediatric subjects who complete the urodynamic procedure
- H_A : Clinicians rate T-DOC® 5 Fr vesical and abdominal catheter as effective for measuring urodynamic pressure in $> 75\%$ of enrolled pediatric subjects who complete the urodynamic procedure

The study will be declared a success if both null hypotheses for safety and efficacy are ruled out.

Secondary Endpoint

In the statistical analysis plan, adjustments are made to the approach that will be followed to evaluate the secondary endpoint to reflect that the goal is to qualitatively describe users' interactions with a device as described in regulatory guidance for usability testing (*FDA's guidance- 'Applying Human Factors and Usability Engineering to Medical Device's, 2016*). Clinical users who have performed three or more procedures with the T-DOC® 5 Fr catheters, shall rate the T-DOC® 5 Fr catheter usability performance on a scale of 1-5 for the clinical user questionnaire, comparing their experience with use of their currently used uroynamics catheter. Responses of 3, 4, or 5 will be tallied as a positive result while responses of 1 or 2 will be tallied as a negative result.

Since there will be 5 responses at most for each of the questions for the secondary endpoint, and the results are thus not well-suited to statistical analysis, hypothesis testing is not appropriate. Instead, the proportions of positive and negative results will be summarized and analysed using descriptive statistics.

Exploratory Analysis

Exploratory Analysis for Discomfort/Pain

To satisfy the first exploratory endpoint (subject experience), a categorical response variable using the Wong-Baker scale from 0 ("No Hurt") to 10 ("Hurts worst") will be used. Subjects will grade their discomfort/pain on the Wong-Baker scale from 0 ("No Hurt") to 10 ("Hurts worst"). of 1, 2, 3, 4, or 5 will be tallied as a positive result while responses of 6, 7, 8, 9, or 10 will be tallied as a negative result.

Because the subjects range in age from 2-12 years, the number of subjects capable of providing feedback on the Wong-Baker scale is anticipated to be limited (≤ 10 is expected). Due to this uncertainty, no formal hypothesis testing will be performed. However, the binary endpoint described above as well as the mode and frequency distribution of the Wong-Baker scale will be used to summarize the results.

Exploratory Analysis for Insertion Depth

To satisfy the second exploratory endpoint, subject data including gender, age, height, weight, adverse events during or immediately following the test and 5-7 days follow-up, catheter insertion depth will be collected as objective evidence on each patient's CRF, where insertion depth is considered the response variable and assumed to be influenced by gender, age, height, weight and/or BMI.

Regression testing can be used to examine the relationship between the insertion depth and collected data (gender, age, height, weight and BMI). The collected data will also be reported using graphical tools based on gender, age, height, weight and BMI. T-tests for differences in insertion depth based on subgroups (male and female, above and below the median height, weight and BMI) will be performed if appropriate.

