9 ASSESSMENT OF INVESTIGATIONAL DEVICE

9.1 Endpoints

OBJECTIVES	ENDPOINTS	JUSTIFICATION FOR ENDPOINTS
Primary		

To confirm the T-DOC® 5Fr vesical and abdominal catheters as a safe and effective means of measuring urodynamic pressure in pediatric subjects 12 years of age and younger.
	
The primary endpoint will be measured by recording the clinician safety and effectiveness rating for each patient on their CRF. The clinician will indicate whether the T-DOC® 5 Fr vesical and abdominal catheters are safe and effective for measuring urodynamics pressure in at least 95% of patients enrolled.
	
Given the intended use of the device, and the fact that there is no single or combination of objective measures generated from the urodynamics test that can establish the safety and effectiveness, it is justified to obtain clinician feedback via a binomial response whether the device was safe and/or effective for measuring urodynamic pressure.

Secondary		

To evaluate the usability of the device by collecting subjective feedback using defined ordinal scales: ease of use, ease of insertion, presence of artefacts, stability of the tracing, perceived time savings, ease of voiding around catheter, presence of use errors and overall satisfaction.
	
The usability performance endpoint will be captured in a questionnaire format. At least 80% of trained clinical users shall rate the T-DOC® 5 Fr performance as 3.0 or better (on a scale of 1-5) on the study outcome questionnaire.
	
When evaluating the usability of a device, the Sponsor feels its appropriate to use a subjective ordinal scale response while evaluating human and device usability factors.

Tertiary/Exploratory		

To explore whether the newly designed, smaller sized T-DOC® 5 Fr catheters causes undue
	
This exploratory endpoint will be measured by collecting patient feedback (within the abilities of
	
Given the patient population, use of the Wong-Baker face

OBJECTIVES	ENDPOINTS	JUSTIFICATION FOR ENDPOINTS

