9.2 Methods of Assessment

A T-DOC® 5 French air-charged catheter will be used to assess and record bladder and abdominal pressures which are in turn used by the clinician to identify urodynamic events. These measurements will be recorded using a LABORIE urodynamics system. The resulting interpretations regarding safety, effectiveness, and usability will be made by the physician overseeing the subject’s case. Patients capable of providing feedback regarding their level of discomfort experienced during the procedure with the T-DOC® 5Fr vesical and abdominal catheters will be presented with copies of the Wong-Baker scale from 0 (“No Hurt”) to 10 (“Hurts worst”) and asked questions by clinic staff who will record their responses on form TDOC5Fr-PEDS-01-CRF4. Subjects will respond to the questions on a scale of 1 through 10.

All study outcome data captured will be compiled and analysed by the LABORIE study team to determine if the endpoints were successfully achieved based on whether the null hypotheses were accepted or rejected.

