12 STATISTICAL CONSIDERATIONS

12.1 Primary Endpoint

In order to satisfy the primary endpoint, each subject CRF will include a binomial question regarding clinician acceptance of the device as being both safe and effective. According to the risk determination outlined in section 4.4 Assessment of Risks and Adverse Device Effects, no more than minimal risk is foreseen for the subject by participating in this study. Given this, the allowable Type I error (α) will be 5% (1-confidence), such that the clinician will grade the device as being safe and effective for 95% of subjects enrolled in this study. Whereas the corresponding Type II error is estimated at 10% (reliability). As stated earlier, safety and effectiveness will be evaluated separately via the following sets of hypotheses:

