13.3 Data Handling

A list of individuals will be maintained who are authorized to make any changes to the data. Data will be reviewed by the Sponsor (outside of monitoring personnel), and requests for clarification and/or corrections will be made through the monitor. Once the review is conducted, the database will be considered clean and ready for analysis. Missing values will remain missing, i.e. no attempt will be made to input missing values and only observed values will be used in data analyses and presentations.

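### The SAP's primary endpoint and hypotheses count only children who complete the procedure, but its exclusion rule implies that children stopped for a catheter-related reason stay in

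*SAP*

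**What the plan says.** **Wording that refers to completers (SAP).**
- Study Objectives and Endpoints: the clinician's primary rating is taken "in patients who enrolled and completed the urodynamic procedure".
- Primary Endpoint: the null and alternative hypotheses, for safety and for effectiveness, each concern a share "of enrolled pediatric subjects who complete the urodynamic procedure".
- Analysis revisions from the protocol, first sentence: "All subjects enrolled and completed the urodynamic procedure will be considered in the final analysis".

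**Wording that points the other way (SAP).** The next sentence of Analysis revisions from the protocol excludes two groups and allows them to be replaced: enrolled children who never undergo the procedure, and children who begin it and do not complete it "for any reason determined by the investigator to be unrelated to the T-DOC® 5 Fr catheters".

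**Scoring.** Protocol 9.1 measures the primary endpoint by "recording the clinician safety and effectiveness rating for each patient on their CRF", and Protocol 12.1 says that "each subject CRF will include a binomial question regarding clinician acceptance of the device". Protocol 13.3 does not impute: "only observed values will be used in data analyses and presentations".

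**Other rules that bear on this.** Protocol 12.6 considered all enrolled subjects, and the SAP revises that. Protocol 7.6 lets subjects who withdraw be replaced. The SAP declares success only if both null hypotheses are rejected, each at one-sided 5% against a rate of 75% or less. Enrolment is 28 to 33 (Protocol 7.4 and 12.4).

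**The concern.** A procedure that stops because of the catheter is direct evidence on whether the device works. Whether that child is in the denominator should be fixed before anyone sees the data. The SAP leaves two defensible answers. An analyst who follows the hypotheses drops the child without departing from the plan; an analyst who follows the exclusion rule keeps the child, also without departing from it.

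The study is single-arm and unblinded, and the investigator judges relatedness. With 28 to 33 children, one or two can decide a primary test. For effectiveness, the more lenient reading favours the device whenever the dropped child would have been rated not effective.

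A smaller gap sits beside this one. A catheter that could not be placed might count as never undergoing the procedure or as beginning it. The condition about relatedness appears to attach only to the second group, so the classification could decide whether a failed placement is counted.

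**Working it through.** **1. Set the passages side by side.** Take a child whose procedure is begun and stopped for a catheter-related reason.
- Endpoint and hypotheses: the child did not complete, so is outside both tests.
- Exclusion rule: the reason is not device-unrelated, so the child is not removed.
- First sentence of the same section: it includes completers but does not say that only completers are included, so it does not settle the matter.

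The condition in the exclusion rule has a purpose only if catheter-related non-completers stay in. This is an inference, though the natural one; no sentence says so outright.

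**2. The plan's own sample size.** Protocol 12.4: n = ln(1 − 0.95)/ln(0.90) = 28.43, stated as 28. It reproduces apart from rounding (rounding up gives 29). The maximum is 33.

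**3. Pass thresholds.** The SAP names no test, so an exact binomial test is assumed: p = P(X ≥ x | n, 0.75) = Σ C(n,j) 0.75^j 0.25^(n−j), j = x to n; pass if p ≤ 0.05. The smallest passing counts are 26/28 (0.0166), 26/29 (0.0455), 27/30 (0.0374), 28/31 (0.0307), 29/32 (0.0252) and 30/33 (0.0205).

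**4. Effect of one dropped child who would have been a failure on the test shown.**

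| Kept | p | Dropped | p |
|---|---|---|---|
| 26/30 | 0.098 | 26/29 | 0.046 |
| 27/31 | 0.083 | 27/30 | 0.037 |
| 28/32 | 0.070 | 28/31 | 0.031 |
| 29/33 | 0.059 | 29/32 | 0.025 |

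Each row goes from fail to pass. This happens only near the threshold: 28/30 (p=0.011) passes whether or not one failure is dropped.

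**5. Effect of one dropped child who was rated safe.** With 29 children and 26 rated safe, p=0.0455, a pass. Dropping one child who was rated safe gives 25/28, p=0.055, a fail. The safety result can therefore move against the device.

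**6. Illustration of the overall effect.** The inputs are assumptions. True success per attempted child is exactly 75%. A share d of attempts are catheter-related stops, all of them failures on the test in question, and all are dropped and replaced until 28 children complete or 33 have been attempted. Success among completers is then 0.75/(1 − d). An exact recursion over attempts gives:

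| d | Success among completers | Chance of passing one test |
|---|---|---|
| 0 | 0.750 | 0.017 |
| 5% | 0.789 | 0.047 |
| 10% | 0.833 | 0.135 |
| 12.5% | 0.857 | 0.225 |

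Success needs both tests, so the study-level chance is at most the per-test figure.

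**The case against.** The strongest reply is that the exclusion rule already settles the question. It is the one sentence that removes anyone, it sits in the section that defines the analysis set, and its condition would be idle if catheter-related stops were dropped anyway. On that view the endpoint and hypotheses are merely loosely worded. Much of this stands: the exclusion rule is probably what was intended. But the hypotheses define what is tested, and they say something else.

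A reader might infer that both success rates are inflated. The documents do not support that. Safety and effectiveness are separate ratings, and a procedure stopped for a poor tracing or a malfunction could still be rated safe. Step 5 shows that dropping such a child can cost the device its safety result.

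A reader might also infer that retained non-completers could not be scored. That goes too far. Each subject's CRF carries the rating question, and under Protocol 9.2 "The resulting interpretations regarding safety, effectiveness, and usability will be made by the physician overseeing" the case. Under Protocol 12.6 the monitor follows up incomplete CRFs. What remains is narrow: a retained child whose rating is still missing would drop out under Protocol 13.3.

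On replacement, the SAP attaches it only to the excluded group, and a child whose test is stopped but who still has the follow-up call is not clearly withdrawn under Protocol 7.6. One sentence in the SAP would remove the doubt.

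Finally, removing children never exposed to the device is reasonable, and adverse events and device deficiencies are recorded either way (Protocol 10.2).

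**Conclusion.** The conflict is real and high confidence is warranted for it: endpoint and hypotheses leave catheter-related non-completers out, while the exclusion rule implies that they stay in. It should be fixed because it leaves open a choice that could decide a primary test.

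The upward bias is established for effectiveness only, and only when the dropped children would be rated not effective. For safety the direction depends on each child's rating.

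The size near the threshold is one child at 30 to 33 started, given an exact binomial test. The overall figures of about 5%, 13% and 22% are an illustration. They rest on a true success rate of exactly 75% per attempt and on assumed stop rates of 5%, 10% and 12.5%, since the documents give none. At 5% the chance is still within the nominal level.

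A reader might take these as an inflated type I error of the SAP's stated test. They are not. They are errors relative to success per attempted child, whereas the stated null concerns completers.

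**What to change.** Before database lock, which the SAP allows, revise the SAP so that the endpoint, the analysis-set paragraph and the four hypotheses name one population: enrolled children in whom the procedure was begun, meaning that placement of a T-DOC 5 Fr catheter was attempted, including failed placement, except those who did not complete for a documented device-unrelated reason.

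State that catheter-related non-completers:
- stay in the denominators of both tests;
- are not replaced;
- are scored by the clinician's CRF ratings for safety and for effectiveness.

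List every exclusion and replacement with its reason.

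Optional: a sensitivity analysis that counts catheter-related non-completers, including any with a missing rating, as not effective. Making that score compulsory in the primary analysis would override the clinician rating that defines the endpoint, and is not needed to reconcile the text.

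**Cost.** A short SAP revision, with no new procedures for the children. Protocol 7.6 need not change if the SAP states the replacement rule, which avoids an amendment and IRB review. The reason for each non-completion must be documented, whereas Protocol 7.6 asks for a withdrawal reason only where possible. Observed success rates may be slightly less favourable.
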